8.1 ANTICIPATED RISKS

a. Medical risks, listing all procedures, their major and minor risks and expected frequency.

We do not anticipate major risk or discomfort beyond that associated with the conventional procedure.

1) Perforation: Only physicians specially trained in EUS will be performing these procedures. The exact risk is minimal (<1%).

2) Infection: It is not standard practice to give antibiotics to all patients prophylactically for either percutaneous liver biopsy or EUS-FNA of non-cystic lesions. Therefore, no subjects will receive antibiotics prophylactically for EUS sampling except those patients at risk for infective endocarditis according to American Heart Association guidelines.

3) Bleeding: The exact risk is minimal (1 in 5,000 chance). Doppler examination will be performed under EUS guidance prior to biopsy to ensure that the needle does not traverse a blood vessel. As a precautionary measure, furthermore, all patients will have PTT, PT/INR, hemoglobin, and platelet count checked prior to the procedure. Those below acceptable standards will not be offered inclusion into the study. Frequent vital signs will be measured and recorded. If vital signs are abnormal and prolonged, a repeat CBC and possibly CT scan will be performed after procedure to ensure the absence of internal or external hemorrhage. These measures should ensure any clinically significant hemorrhage is detected and treated in a timely manner.

4) Pancreatitis: Will be detected by the presence of pain with or without nausea and vomiting after pancreatic biopsy. If present, the patient will be hospitalized, kept NPO, and receive IV hydration.

 b. Steps taken to minimize the risks.
 Adherence to the standard of practice of the Johns Hopkins Hospital Division of Gastroenterology will be kept (as described in part a).

- c. Legal risks such as the risks that would be associated with breach of confidentiality. There are no legal risks associated with participation in this study. All measures to protect confidentiality will be taken.
- d. Financial risks to the participants. None.

9. ADVERSE EVENT REPORTING REQUIREMENTS

9.1 Definitions

9.1.1 Adverse Event (AE)

An adverse event (AE) is any undesirable sign, symptom or medical condition or experience that develops or worsens in severity after the procedure, even if the event is not considered to be related to the study.

Abnormal laboratory values or diagnostic test results constitute adverse events only if they induce clinical signs or symptoms or require treatment or further diagnostic tests.

9.1.2 Serious adverse event (SAE)

A serious adverse event (SAE) is any adverse event and regardless of causality that:

- Results in death
- Is life-threatening. Life-threatening means that the person was at immediate risk of death from the reaction as it occurred, i.e., it does not include a reaction which hypothetically might have caused death had it occurred in a more severe form.
- Prolongs inpatient hospitalization (prolonged a hospitalization beyond the expected length of stay). Hospitalization admissions and/or surgical operations scheduled to occur during the study period, but planned prior to study entry are not considered SAEs if the illness or disease existed before the person was enrolled in the trial, provided that it did not deteriorate in an unexpected manner during the trial (e.g., surgery performed earlier than planned
- Results in persistent or significant disability/incapacity. Disability is defined as a substantial disruption of a person's ability to conduct normal life functions.
- Is a congenital anomaly or birth defect; or
- Is an important medical event when, based upon appropriate medical judgment, it may jeopardize the participant and require medical or surgical intervention to prevent one of the outcomes listed above.

Events not considered to be serious adverse events are hospitalizations for:

- routine treatment or monitoring of the studied indication, not associated with any deterioration in condition, or for elective procedures
- elective or pre-planned treatment for a pre-existing condition that did not worsen
- emergency outpatient treatment for an event not fulfilling the serious criteria outlined above and not resulting in inpatient admission
- 9.2 Procedures for AE and SAE Recording and Reporting

Participating investigators will assess the occurrence of AEs and SAEs at all participant evaluation time points during the study.

All AEs and SAEs whether reported by the participant, discovered during questioning, directly observed, or detected by physical examination, laboratory test or other means, will be recorded in the participant's medical record and on the appropriate study-specific case report forms.

The description and the grading for the adverse events will be done according to ASGE severity scale.

9.3 Reporting Requirements

Each investigative site will be responsible to report SAEs that occur at that institution to their respective IRB. It is the responsibility of each participating investigator to report serious adverse events to the study sponsor and/or others as described below.

- 9.4 Reporting to the Study Team
 - 9.4.1 Serious Adverse Event Reporting

All serious adverse events that occur after the procedure, during the procedure, or within 30 days of the procedure must be reported to the Principle Investigator on the local institutional SAE form. This includes events meeting the criteria outlined in Section 11.1.2, as well as the following:

- Grade 2 (moderate) and Grade 3 (severe) Events Only events that are unexpected and possibly, probably or definitely related/associated with the intervention.
- All Grade 4 (life-threatening or disabling) Events Unless expected AND specifically listed in the protocol as not requiring reporting.
- All Grade 5 (fatal) Events When the participant is enrolled and actively
 participating in the trial OR when the event occurs within 30 days of the
 last study intervention.
- Progressive disease will be reported within 7 days

Note: If the participant is in long term follow up, report the death at the time of continuing review.

Participating investigators must report each serious adverse event to the overall Principal Investigator within one business day of learning of the occurrence. In the event that the participating investigator does not become aware of the serious adverse event immediately (e.g., participant sought treatment elsewhere), the participating investigator is to report the event within one business day of learning of it and document the time of his or her first awareness of the adverse event.

Report serious adverse events by telephone, email or facsimile to:

[name] [contact] Email: [contact] [contact] Emergency Contact #: [contact] (mobile) Within the subsequent 1-2 business day from initial report, the participating investigator must provide follow-up information on the serious adverse event. Follow-up information should describe whether the event has resolved or continues, if and how the event was treated, and whether the participant will continue or discontinue study participation.

9.4.2 Non-Serious Adverse Event Reporting

Non-serious adverse events will be not be reported Reporting to the Institutional Review Board (IRB)

Investigative sites should report serious adverse events to their respective IRB according to the local IRB's policies and procedures in reporting adverse events. A copy of the submitted institutional SAE form should be forwarded to:

[name] [contact] Email: [contact] [contact] Emergency Contact #: [contact] (mobile)

- 9.5 Reporting to the Food and Drug Administration (FDA) N/A
- 9.6 Reporting to the NIH Office of Biotechnology Activities (OBA) N/A
- 9.7 Reporting to the Institutional Biosafety Committee (IBC) N/A
- **9.8** Reporting to Hospital Risk Management Participating investigators will report to their local Risk Management office any subject safety reports or sentinel events that require reporting according to institutional policy.
- **9.9** Monitoring of Adverse Events and Period of Observation All adverse events, both serious and non-serious, and deaths that are encountered from initiation of study intervention, throughout the study, and within 30 days of the last study intervention should be followed to their resolution, or until the participating investigator assesses them as stable, or the participating investigator determines the event to be irreversible, or the participant is lost to follow-up. The presence and resolution of AEs and SAEs (with dates) should be documented on the appropriate case report form and recorded in the participant's medical record to facilitate source data verification.

For some SAEs, the study sponsor or designee may follow-up by telephone, fax, and/or monitoring visit to obtain additional case details deemed necessary to appropriately evaluate the SAE report (e.g., hospital discharge summary, consultant report, or autopsy report).

Participants should be instructed to report any serious post-study event(s) that might reasonably be related to participation in this study. Participating investigators should notify the Overall Investigator or respective IRB of any unanticipated death or adverse event occurring after a participant has discontinued or terminated study participation that may reasonably be related to the study.

10. DATA AND SAFETY MONITORING

10.1 Data Reporting

Case report forms will be provided for all study mandated data points and should be submitted based on the deadlines detailed in Section 10.1.2

10.1.1 Data Submission

Case report forms should be submitted to the JHBox account

10.2 Auditing/Monitoring

A data safety and monitoring board (DSMB) will be appointed (TBD). The DSMB will be responsible for reviewing all major complications (perforation, hospitalization for > 48 hours, bleeding requiring transfusion, deaths etc). If any serious adverse event is noted during the study then the DSMB will be required to meet.

11. REGULATORY CONSIDERATIONS

11.1 Protocol Review and Amendments

This protocol, the proposed informed consents, all forms of participant information related to the study and any other necessary documents must be submitted, reviewed and approved by a properly constituted IRB governing each study location. This will occur following approval by the Coordinating Center IRB.

Any changes made to the protocol must be submitted as amendments and must be approved by the IRB prior to implementation. Any changes in study conduct must be reported to the IRB. The overall Principal Investigator will disseminate protocol amendment information to all participating investigators.

All decisions of the IRB concerning the conduct of the study must be made in writing.

11.2 Informed Consent

All participants must be provided a consent form describing each portion of this study and providing sufficient information for participants to make an informed decision about their participation in this study. The formal consent of a participant, using the IRB approved consent form, must be obtained before the participant is involved in any study-related procedure. The consent form must be signed and dated by the participant or the participant's legally authorized representative, and by the person obtaining the consent. The participant must be given a copy of the signed and dated consent document. The original signed copy of the consent document must be retained in the medical record or research file.

11.3 Ethics and Good Clinical Practice (GCP)

This study is to be conducted according to the following considerations, which represent good and sound research practice:

- E6 Good Clinical Practice: Consolidated Guidance www.fda.gov/downloads/RegulatoryInformation/Guidances/UCM129515.pdf
- US Code of Federal Regulations (CFR) governing clinical study conduct and ethical principles that have their origin in the Declaration of Helsinki
 - Title 21 Part 11 Electronic Records; Electronic Signatures www.access.gpo.gov/nara/cfr/waisidx_02/21cfr11_02.html
 - Title 21 Part 50 Protection of Human Subjects www.access.gpo.gov/nara/cfr/waisidx 02/21cfr50 02.html
 - Title 21 Part 54 Financial Disclosure by Clinical Investigators www.access.gpo.gov/nara/cfr/waisidx_02/21cfr54_02.html
 - Title 21 Part 56 Institutional Review Boards www.access.gpo.gov/nara/cfr/waisidx_02/21cfr56_02.html

- Title 21 Part 312 Investigational New Drug Application www.access.gpo.gov/nara/cfr/waisidx_02/21cfr312_02.html
- State laws

It is understood that deviations from the protocol should be avoided, except when necessary to eliminate an immediate hazard to a research participant. In such case, the deviation must be reported to the IRB according to the local reporting policy.

11.4 Study Documentation

The investigator must prepare and maintain adequate and accurate case histories designed to record all observations and other data pertinent to the study for each research participant. This information enables the study to be fully documented and the study data to be subsequently verified.

Original source documents supporting entries in the case report forms include but are not limited to hospital records, clinical charts, laboratory and pharmacy records, recorded data from automated instruments, microfiches, photographic negatives, microfilm or magnetic media, and/or x-rays.

11.5 Records Retention

All study-related documents must be retained for the maximum period required by applicable federal regulations and guidelines or institutional policies.

- 11.6 Multi-center Guidelines
 - Overall Principal Investigator/Coordinating Center is responsible for distributing all Safety Reports to all participating institutions for submission to their individual IRBs for action as required.
 - Mechanisms will be in place to ensure quality assurance, protocol compliance, and adverse event reporting at each site.

12. STATISTICAL CONSIDERATIONS

Overview: This study is designed as a non-inferiority trial.

Considering a success rate of 85% in the FNA with ROSE group, based published studies, we selected a non-inferiority margin (∂) of 10%, in accordance with the USFDA recommendations (8). Based on the following formula (9):

n = f(α, β) × [πs × (100 – πs) + πe × (100 – πe)] / (πs – πe – d)2

where πs and πe are the true percent 'success' in the standard and experimental treatment group respectively, and

 $f(\alpha, \beta) = [\Phi - 1(\alpha) + \Phi - 1(\beta)]2$

 Φ -1 is the cumulative distribution function of a standardized normal deviate

We calculated that our trial will require enrolling 120 patients for power of 80% and two sided α of 0.05.

Taking into consideration a 10% dropout rate, the total patients to be enrolled=132

Baseline demographics, pre-, intra- and post-intervention data will be prospectively collected on data collection forms which will be maintained in an electronic database system. Results will be reported as mean ± standard deviation (SD) for quantitative variables and percentages for categorical variables. The groups will be compared using the Student's t- test or Wilcoxon rank sum test for continuous variables and the chi-square test (or Fisher's exact test if required) for categorical variables. To compare

diagnostic accuracy between two EUS sampling techniques, we will use McNemar's test. Statistical significance will be based on two-sided design-based tests evaluated at α = 0.05. All statistical analyses will be performed using STATA.

a. Endpoints:

Primary:

Diagnostic accuracy will be defined as (true positive + true negative)/all samples. The final diagnosis will be based on one of the following criteria: (i) surgical pathology specimen from patients who underwent surgical resection; (ii) cytological or histopathological diagnosis of malignancy in patients with unresectable disease with appropriate imaging and clinical course of disease; (iii) cytological and histopathological diagnosis of benign disease with an appropriate clinical course of disease for minimum of 6 months.

Secondary:

1. Specimen adequacy

This will be defined as the proportion of samples in which a final histopathological diagnosis could be made.

2. Percentage of histology cores obtained

This will be defined as the proportion of samples in which a visible histology core biopsy was obtained

- 3. Number of passes Number of passes required for diagnosis
- 4. Rate of technical failures

Technical failure was defined as the inability to perform the procedure, including the need to change the needle

5. Adverse events

All pre, intra- and immediate post-procedure adverse events will be recorded and rated according to ASGE lexicon for adverse events.

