7. PROCEDURE PLAN

All EUS/FNB and EUS/FNA will be performed using a linear array echoendoscope by one of seven experienced EUS physicians at JHH. All patients will undergo both EUS/FNB and EUS/FNA. Patients will be randomized to either FNB or FNA first by

means of computer-generated numbers. The endoscopist will not be blinded to the randomization; however, the study pathologist will be blinded to randomization.

EUS/FNB will be performed using similar techniques for tissue acquisition as FNA using 22-g FNB needle (Medtronic SharkCore or Boston Scientific Acquire). Lesions will be identified using EUS and punctured with the 22-g FNB needle (10-15 back and forth movements per needle pass, fanning as appropriate). After the lesion is punctured, the stylet will be removed and 10cc suction will be applied. FNB samples will be placed directly into formalin containers and sent to be processed by surgical pathology.

EUS/FNA with ROSE will be performed using standard techniques via 22-g FNA needle (Cook Medical EchoTip Ultra or Boston Scientific Expect or Medtronic Beacon). Lesions will be identified using EUS and punctured with the FNA needle (10-15 back and forth movements per needle pass, fanning as appropriate). After the lesion is punctured, the stylet will be removed and 10cc suction will be applied. FNA specimens will be processed for ROSE using standard techniques with bedside smear slide evaluation and liquid-based cytology and cell-block preparation.

The first randomization assigned EUS sampling technique will be used until adequate specimen is achieved (up to 3 passes total). After 3 passes, the patient will undergo the other EUS sampling technique until adequate specimen is achieved (up to 3 passes total). If inadequate biopsies are obtained after a total of 6 passes (3 with initial tissue acquisition techniques, 3 with the other technique), the endosonographer will be permitted to utilize any EUS sampling technique preferred to obtain a diagnosis during the same procedure or at a later date.

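### The 120 patients and 80% power cannot be derived from the plan: FNB accuracy has no assumed value, and an independent-groups formula is used for a paired design

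*Combined protocol and SAP*

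**What the plan says.** All the sample-size inputs are in section 12 (Statistical Considerations) of the combined protocol and SAP. The trial is described as non-inferiority. The standard arm and the margin are introduced by "Considering a success rate of 85% in the FNA with ROSE group, based published studies, we selected a non-inferiority margin", and the margin is 10 percentage points. The formula is "n = f(α, β) × [πs × (100 – πs) + πe × (100 – πe)] / (πs – πe – d)2". Its symbols are explained as follows: "where πs and πe are the true percent 'success' in the standard and experimental treatment group respectively". The multiplier f(α, β) is printed with α, not α/2. The result is "We calculated that our trial will require enrolling 120 patients for power of 80% and two sided α of 0.05", and then "Taking into consideration a 10% dropout rate, the total patients to be enrolled=132".

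No number is given for πe in section 12 or anywhere else, and the sentence defining it is complete.

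Section 7 (Procedure Plan) says "All patients will undergo both EUS/FNB and EUS/FNA". Sections 1.1 and 7 make clear that randomisation decides only which technique comes first. For the primary comparison, section 12 says that to compare "diagnostic accuracy between two EUS sampling techniques, we will use McNemar's test".

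**The concern.** There are two separate faults, and repairing one does not repair the other.

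1. **Missing input.** A non-inferiority sample size depends heavily on the assumed true difference. Without πe the formula has no value, so a reader can neither check 120 nor know what advantage, if any, was assumed for FNB.
2. **Wrong variance.** The bracket in the formula adds two independent binomial variances. Here each patient supplies a result for both techniques. The variance of the paired difference depends on the discordant proportion, meaning the share of patients in whom one technique is correct and the other is not. The plan gives no such figure.

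The 80% power is the only stated justification for the trial's size. If it has no basis and the trial fails to show non-inferiority, nobody can say whether FNB was worse or the trial was too small.

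**Working it through.** **Inputs from section 12:** πs = 85, d = 10, power 80%, α = 0.05 two-sided, 10% dropout. **Not in the documents:** πe and the discordant proportion ψ. Values of these below are assumptions.

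**Step 1: try to reproduce 120 with the printed formula.**

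- Two-sided 0.05: f = (1.960 + 0.842)² = 7.849.
- 0.05 entered directly, as f(α, β) is printed: f = (1.645 + 0.842)² = 6.183.

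| Assumed πe | Bracket | Denominator | n per group, two-sided 0.05 | n per group, 0.05 in one tail |
|---|---|---|---|---|
| 85 | 1275 + 1275 = 2550 | (−10)² = 100 | 200.1 → 201 | 157.7 → 158 |
| 90 | 1275 + 900 = 2175 | (−15)² = 225 | 75.9 → 76 (152 total) | 59.8 → 60 (120 total) |

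Equal accuracies do not give 120 on either reading. Solving the formula for πe instead:

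| 120 read as | πe needed, two-sided 0.05 | πe needed, 0.05 in one tail |
|---|---|---|
| per group | 87.5% | 86.3% |
| total (60 per group) | 91.4% | 90.0% |

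The only round-number route is πe = 90% with 0.05 in one tail, which gives 2 × 60 = 120. It may be the origin, but that is an inference. It also conflicts with the stated two-sided 0.05, at which the same πe needs 152 in total.

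**Step 2: paired calculation, equal accuracies of 85%.** With a true difference of zero, the pairs needed are n = 7.849 × ψ / 0.10². If the two results were independent within a patient, ψ = 2 × 0.85 × 0.15 = 25.5%.

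For evaluable patients, 132 × 0.9 = 118.8, so 118 complete pairs. The normal-approximation power is Φ(0.10/√(ψ/n) − 1.96). Exact power enumerates the discordant cells and applies the paired score (Tango) test against −10 points at one-sided 0.025.

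| Discordance ψ | Pairs for 80% power (approximation) | Power, 118 pairs (approximation) | Power, 118 pairs (exact) |
|---|---|---|---|
| 10% | 79 | 93% | 89% |
| 15% | 118 | 80% | 77% |
| 20% | 157 | 68% | 65% |
| 25.5% | 201 | 58% | 56% |

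Power crosses 80% at ψ = 13.6% (exact) or 15.0% (approximation) for 118 pairs, and at 13.4% or 15.3% for 120 pairs.

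**Step 3: paired calculation if FNB is truly better.** Exact power for 118 pairs:

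- πe = 87.5%: 98%, 92%, 84% and 78% at ψ = 10%, 15%, 20% and 23.75%. The last is independence: 0.85 × 0.125 + 0.875 × 0.15.
- πe = 90%: 99%, 95% and 93% at ψ = 15%, 20% and 22%. The last is independence: 0.85 × 0.10 + 0.90 × 0.15.

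Across these scenarios power runs from about 56% to 99%, driven entirely by two quantities the plan does not state.

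**The case against.** The best defence is that the error leans the safe way. If n is read as the number of pairs, and results within a patient are positively correlated or independent, the independent-groups variance is an upper bound. In a paired design 120 patients do supply 120 results per technique, so 120 per group is a natural reading. It corresponds to πe of about 87.5%, and at that value the trial has close to 80% power or more all the way up to independence. On this view the plan has a documentation gap and no shortfall, and enrolment need not change.

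Much of this is right. The formula is conservative in that sense, a shortfall is not demonstrated, and the 13% to 15% cut-off applies only if the accuracies are equal. But the defence depends on a 2.5-point FNB advantage that the plan neither states nor justifies. With equal accuracies the same 120 may be too few.

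Two smaller points. Because the denominator is squared, the formula can also return 120 per group with FNB accuracy near 60%, but such values lie beyond the margin and mean nothing for non-inferiority. It could also be said that the choice of primary test is a separate matter. It is distinct, but power has to be calculated for the test that decides the claim, and McNemar's test of equality does not use the 10-point margin.

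**Conclusion.** The concern holds and should be fixed before the sample-size statement is relied on. From the plan's own inputs, 120 patients and 80% power cannot be obtained: πe is missing, the variance does not match the design, and the discordance needed for a paired calculation is absent. With equal accuracies the printed formula gives 201 or 158 per group, depending on how α enters.

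This does not show that the trial is too small. If both accuracies are 85% and the decision uses a two-sided 95% limit, 120 patients are enough up to about 13% to 15% discordance and too few above it. If FNB is truly 90% accurate, power exceeds 90% throughout the 15% to 22% discordance range examined. The values of πe and discordance used here are assumptions, and the documents do not say which apply.

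**What to change.** Keep enrolment at 132. In section 12:

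1. State πe with its source, whether α is one- or two-sided, and the assumed discordance. If πe = 90% or 0.05 in one tail was used, declare and justify it.
2. Replace the independent-groups formula with a named paired non-inferiority method, and give power over a range of discordance.
3. Tie the calculation to the decision rule. Possible text:

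> Non-inferiority is concluded if the lower limit of the two-sided 95% score interval for the paired difference in accuracy (FNB minus FNA) lies above −10 points. This replaces McNemar's test as the primary criterion; McNemar's test is kept as a secondary test of difference. With 132 enrolled and 10% dropout, about 118 pairs are evaluable. If both accuracies are 85%, exact power is about 89%, 77%, 65% and 56% at 10%, 15%, 20% and 25.5% discordance.

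The score interval is one suitable choice; another paired interval would serve if power is computed for it.

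**Cost:** a protocol amendment with IRB approval (section 11.1), because the stated primary test changes along with the power text. No extra patients are needed. The sponsor gives up an unconditional 80%: power becomes conditional on πe and discordance, and may be below 80% if accuracies are equal and discordance exceeds about 13% to 15%.

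### The printed non-inferiority formula puts all of α in one tail while the only α given is two-sided 0.05, and no section states the error level or interval for judging the 10-point margin

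*Combined protocol and SAP*

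**What the plan says.** Everything on this point is in section 12 (Statistical Considerations) of the combined protocol and SAP.

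- **Hypothesis and margin.** "This study is designed as a non-inferiority trial", and "we selected a non-inferiority margin (∂) of 10" percent.
- **Rates.** "Considering a success rate of 85% in the FNA with ROSE group". The FNB rate appears only as a symbol ("where πs and πe are the true percent 'success' in the standard and experimental treatment group respectively"), with no value.
- **Formula.** "n = f(α, β) × [πs × (100 – πs) + πe × (100 – πe)] / (πs – πe – d)2", where f(α, β) is the square of the bracket printed as "\Phi - 1(\alpha) + \Phi - 1(\beta)]2". The quantile is taken at α, not at α/2.
- **Level for sample size.** "We calculated that our trial will require enrolling 120 patients for power of 80% and two sided α of 0.05".
- **Level for analysis.** "Statistical significance will be based on two-sided design-based tests evaluated at α = 0.05". The test named for diagnostic accuracy is McNemar's.

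No section gives a one-sided level, a confidence level for an interval to set against the margin, or any other rule for declaring non-inferiority. Section 7 (Procedure Plan) has every patient sampled by both techniques, so the comparison is paired.

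**The concern.** A non-inferiority claim rests on one tail: the risk of accepting FNB when it is truly worse than FNA by the full margin. If 0.05 is entered in the formula as printed, that risk is 5%, which corresponds to the lower limit of a 90% interval. A two-sided 0.05, as the text labels it, normally means 2.5% in that tail and a 95% interval. The formula and its label therefore disagree when read literally.

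The analysis paragraph does not resolve this. McNemar's test asks whether the two techniques differ, and a non-significant result does not show that a 10-point deficit has been excluded. The interval level for the margin would have to be chosen by the analyst, possibly after the data are seen. The claim it protects is that on-site cytopathology can be dropped without loss of diagnostic yield.

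**Working it through.** **Inputs from section 12:** FNA 85%, margin 10 points, power 80%, α 0.05, N 120 before dropout. **Assumptions:** the FNB rate (not stated), the proportion of discordant pairs (not stated), and a Wald interval for the paired difference (no interval is specified).

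**1. Does the plan's formula return 120?**

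- 5% in one tail: f = (1.645 + 0.842)² = 6.18.
- Two-sided 0.05: f = (1.960 + 0.842)² = 7.85.

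n per group = f × [85×15 + πe×(100 − πe)] / (85 − πe − 10)²

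| Assumed FNB rate | 5% in one tail | Two-sided 0.05 |
|---|---|---|
| 85% | 6.18 × 2550/100 → 158 per group, 316 total | 7.85 × 2550/100 → 201 per group, 402 total |
| 90% | 6.18 × 2175/225 = 59.8 → 60 per group, **120 total** | 7.85 × 2175/225 = 75.9 → 76 per group, 152 total |
| about 87.5% (87.46%) | not 120 | 7.85 × 2371.7/155.3 = 119.9 → **120 per group** |
| about 91.4% (91.415%) | not 120 | 7.85 × 2059.8/269.5 = 60.0 → 60 per group, **120 total** |

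The stated inputs alone do not reproduce 120. Among whole-percent FNB rates from 85% to 92%, only 90% with 5% in one tail gives it. Rates near 87.5% or 91.4% give it at two-sided 0.05. The figure is therefore compatible with either level.

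**2. Can the level change the conclusion?** Take 120 pairs, with 13 correct on FNA only and 10 correct on FNB only.

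- Difference, FNB minus FNA = (10 − 13)/120 = -2.5 points.
- SE = √(23 − 9/120)/120 = 3.99 points.
- 90% interval: lower limit = -2.5 − 1.645×3.99 = -9.1, above -10, passes.
- 95% interval: lower limit = -2.5 − 1.960×3.99 = -10.3, below -10, fails.
- McNemar's statistic: z = 3/√23 = 0.63, not significant, and silent on the margin.

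The range of observed FNB deficits that pass at 90% and fail at 95% comes from solving D − z√((disc − D²)/120) = -0.10, where disc is the discordant proportion.

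| Discordant pairs (assumed) | Deficit that passes at 90% and fails at 95% |
|---|---|
| 15% | 3.1 to 4.2 points |
| 20% | 2.0 to 3.3 points |
| 30% | 0.2 to 1.8 points |

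**3. False non-inferiority.** With a true 10-point deficit, 20% discordance and 120 pairs (400,000 simulated trials), the rate is 5.6% with the 90% interval and 3.3% with the 95% interval. The ratio is 5.6/3.3 = 1.7.

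**4. Power of 120 pairs at one-sided 2.5%, 20% discordance.**

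- FNB 90%: SE = √((0.20 − 0.0025)/120) = 0.0406; Φ(0.15/0.0406 − 1.960) = about 96%.
- FNB 85%: SE = √(0.20/120) = 0.0408; Φ(0.10/0.0408 − 1.960) = about 69%.

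**The case against.** The strongest defence is that both numerical statements of α in the plan are two-sided 0.05, and that the formula is symbolic. If α in f(α, β) is taken as the per-tail value 0.025, formula and label agree. A planning formula is also not an instruction for the analysis. This largely stands. The mismatch is in the notation as printed, and a reader who infers that the plan contains two competing decision rules goes beyond the text. What remains is that the plan never says α is a per-tail value, the only number it attaches to α is 0.05, and the analysis paragraph supplies no rule for the margin.

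A second defence is that the borderline figures rest on an interval the plan does not specify. That is true, and they are labelled as assumptions. They show that the choice can matter, not what the trial will find.

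A third is that the missing decision rule is the larger gap. I agree: correcting the notation alone would leave the non-inferiority decision undefined, so the fix has to cover both.

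**Conclusion.** The point holds as a mismatch between the printed formula and the stated level, together with an undefined error level for the 10-point margin. Under the stated assumptions (120 pairs, Wald interval, 20% discordance), observed FNB deficits of 2.0 to 3.3 points would be judged differently at the two levels, and the false non-inferiority rate would be 5.6% or 3.3%.

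Two stronger readings are tempting and are not supported.

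- *That the trial was sized at one-sided 5%.* The neat match at an assumed FNB rate of 90% suggests it. No FNB rate is stated, however, and rates near 91.4% or 87.5% return 120 at two-sided 0.05.
- *That the trial has only about 70% power at two-sided 0.05.* That figure, Φ(15/√(2175/60) − 1.960) = 0.70, is for 60 versus 60 independent patients. Section 7 gives 120 pairs, whose power depends on the FNB rate and discordance: about 96% or about 69% in the two cases worked above.

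**What to change.** In section 12:

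1. Keep the stated two-sided 0.05 and replace Φ-1(α) with Φ-1(α/2) in f(α, β).
2. Add the decision rule: non-inferiority is declared only if the lower limit of the two-sided 95% confidence interval for the paired difference in diagnostic accuracy (FNB minus FNA) is above -10 points. Name the interval method. McNemar's test may stay as a test of difference, but not as the basis for non-inferiority.
3. State the assumed FNB rate and proportion of discordant pairs, and restate the power of 120 pairs at this level. Do not quote the unpaired 70%.

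The cost is wording plus one recalculation. The downside is a slightly stricter criterion than a 90% interval and a stated power that may be less favourable than 80% if FNB is assumed no better than FNA.
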